Study Protocol and Statistical Analysis Plan for NCT03750968

Lutein & Zeaxanthin in Pregnancy – Carotenoid Supplementation during Pregnancy: Ocular and Systemic Effects

The following pages contain the IRB approved study protocol and statistical analysis plan at the most recent renewal approved on 21 December 2022.

Date: Tuesday, May 2, 2023 2:01:03 PM

[Print](#)
[Close](#)
IRB_00116610
Created: 10/1/2018 12:13 PM

IRB_00116610

1. Contacts and Title

PI: [name]

Submitted: 11/21/2018

Title: Lutein & Zeaxanthin in Pregnancy (L-ZIP) - Carotenoid Supplementation During Pregnancy: Ocular and Systemic Effects

1. Study Introduction

1. Responsible Investigator:

[name]

Email	Training	Col Date
[contact]	7/27/2021 MCG	4/3/2023

a. Position of the Investigator:

- Faculty or Non-Academic Equivalent
- Student
- Staff
- Resident/Fellow
- Other

2. Contact Persons for the Responsible Investigator:

Name	Email	Training
[name]	[contact]	1/30/2023 MCG
[name]	[contact]	CG
[name]	[contact]	1/31/2023 MCG
[name]	[contact]	1/4/2023 MCG
[name]	[contact]	6/17/2022 MCG

3. Guests of the Responsible Investigator:

Last Name	First Name	E-Mail
-----------	------------	--------

There are no items to display

4. What type of application is being submitted?

[New Study Application](#) (or Amendment/Continuing Review)

5. Title Of Study:

Lutein & Zeaxanthin in Pregnancy (L-ZIP) - Carotenoid Supplementation During Pregnancy: Ocular and Systemic Effects

6. Study Purposes and Objectives:

The primary objective of this study is to characterize the carotenoid status of mothers during pregnancy, specifically to determine if prenatal supplementation counteracts maternal systemic and ocular carotenoid depletion.

The primary outcome measure will be change in carotenoid levels from enrollment to final study visit (birth of child) as measured in serum, skin and the macula by high-performance liquid chromatography (HPLC), resonance Raman spectroscopy, and macular pigment imaging, respectively.

7. Is this a multi-site study, where more than one site needs IRB approval?

Yes No

8. Background and Introduction:

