Has the participant selection process overprotected potential subjects who are considered vulnerable so that they are denied opportunities to participate in research?

Yes No

4. Number of participants to be included and/or enrolled in this entire study, across all study locations: 60 mothers and 60 infants

At Utah prior to October 2019: 60 mothers and 60 infants

5. Characteristics of Participants/Inclusion Criteria:

Pregnant women, 18 or older of all races and ethnicities who:

- have an uncomplicated obstetric history
- plan to deliver either vaginally or by Caesarian section at the University of Utah for their current pregnancy

6. Participant Exclusion Criteria:

Women will be excluded if they:

- Have regularly taken carotenoid supplements containing more than 0.5 mg of lutein and/or zeaxanthin daily during the past six months.
- Have significant eye disease associated with macular pigment abnormalities such as Stargardt disease, albinism, or macular telangiectasia type II (MacTel).
- Have any conditions associated with high-risk pregnancies such as adolescent pregnancy, multiparity, current or past history of diabetes, pre-eclampsia, previous premature delivery, drug abuse, or other significant medical illness.

7. Is a substantial percentage of the participant population anticipated to be non-English speaking?

Yes No

Title: Lutein & Zeaxanthin in Pregnancy (L-ZIP) - Carotenoid Supplementation During Pregnancy: Ocular and Systemic Effects

Vulnerable Populations

Justification Requirements for the Inclusion of Vulnerable Populations

1. How does the nature of the research require or justify using the proposed subject population?

The main objectives of the study are to describe mothers' carotenoid status during pregnancy, and the relation between maternal nutritional status and its effect on the newborn.

2. Would it be possible to conduct the study with other, less vulnerable subjects?

Yes No

If yes, justify the inclusion of vulnerable subjects:

3. Is this population being included primarily for the convenience of the researcher?

Yes No

If yes, explain:

Title: Lutein & Zeaxanthin in Pregnancy (L-ZIP) - Carotenoid Supplementation During Pregnancy: Ocular and Systemic Effects

4. Study Information

1. Design of Study (select all that apply):

Non-Experimental and/or Descriptive Research Design:

There are no items to display

Experimental and/or Interventional Research Design:

Blinded Trial (Single or Double Blinded)

Randomized Trial

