Phase II Clinical Trial

Development of a research resource (repositories, databases, etc.)

There are no items to display

Other

2. Does your study involve the use of any placebo?

Yes No

3. Length of entire study, from initiation through closeout:

2 years

4. How will participants be recruited or identified for inclusion in the study?

a. Select all methods that will be used:

In-person contact (e.g., patients, students, etc.)

Written or electronic record review

Written advertising (flyers, brochures, website postings, newspaper ads, etc.)

b. Describe the recruitment/participant identification process in detail (e.g. who will review charts or records, who can refer participants to the study, where will flyers be posted, how often will recruitment letters be sent, when will follow-up phone calls be made, etc.):

Mothers who are eligible for the study will be recruited from the OB/GYN Clinics of the University of Utah during a first trimester prenatal visit (prior to week 13), with agreement from their attending Obstetrician.

Recruitment brochures will be posted in clinic areas.

A web-based tool, the Human Subjects Recruitment Tool (HSRT), will be used to screen for potential patients who meet the IRB approved eligibility requirements **and** have a clinic appointment/inpatient visit at one of the approved clinic and/or inpatient locations.

We will also screen patient appointment logs through a Waiver of Authorization to identify potential patients who meet initial eligibility criteria.

Potential participants will then be approached about the study during one of their prenatal clinic visits. Study personnel will describe the study in detail and review the study protocol with the patient.

Data from the Human Subjects Recruitment Tool (HSRT) will become unavailable the day the IRB expires or when the research team notifies the EDW that the recruitment period closes.

5. How will consent be obtained?

Informed Consent Process (with or without a document)

6. Describe all the procedures chronologically, from screening/enrollment through study closeout, which will be completed in the research project.

Study Visit Schedule

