Initial evaluation of each mother's carotenoid status will be obtained prior to starting any study supplements. Subsequent evaluations while participants are taking the study supplements will be performed in conjunction with routine prenatal visits to their Obstetrician, at approximately 22-26 weeks gestational age and again at 37-39 weeks gestational age. All mothers will undergo a final assessment within two weeks of giving birth.

Infants' evaluations will be performed in the first two weeks of life, either during the original hospital stay or at a follow up outpatient clinic visit.

Visit:	Screening/ Baseline	Maternal Supplementation		
	T1	T2	T3	Birth
Timeframe:	Before 14 Wks GA	22-26 Wks GA	37-39 Wks GA	0 to 2 Wks
Informed Consent	X			
Randomization	X			
Maternal visual acuity and contrast sensitivity	X	X	X	X
Maternal nutritional surveys	X	X	X	X
Dilated eye examination	X			
Maternal serum carotenoids	X	X	X	X
Maternal macular pigment imaging	X	X	X	X
Maternal skin carotenoids	X	X	X	X
Dispense prenatal supplement and do pill counts	X	X	X	X
Infant cord blood carotenoids				X
Infant macular pigment imaging				X
Infant foveal imaging (sdOCT)				X
Infant skin carotenoids				X

Unscheduled Visits

Mothers may be seen for Unscheduled Visits if deemed necessary for repeat measurements or follow-up of Adverse Events. If a mother delivers her baby prematurely, she and her infant will remain in the study and will be asked to complete the final study visit.

Description of Study Assessments:

Visual Function - Manifest refraction, and measurement of best-corrected visual acuity and contrast sensitivity of the mothers will be obtained by certified ophthalmic technicians using standardized protocols. The study staff performing visual acuity will be masked to the treatment assignment. Best-corrected visual acuity testing will be assessed on ETDRS back-lit charts starting at a distance of 4 m, and should precede any examination requiring administration of eye drops to dilate the eye or any examination requiring contact with the eye. Contrast sensitivity will be measured by the Pelli-Robson threshold contrast sensitivity chart at 1 m.

Maternal Eye Exam - The complete ophthalmic exam will consist of the following:

- External examination of the eye and adnexa.
- Routine screening for eyelids/pupil responsiveness (including ptosis, abnormal pupil shape, unequal pupils, abnormal reaction to light and afferent pupillary defect).

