Statistical power and sample size (N) for one of the primary outcome measures, maternal skin carotenoids at birth, was determined using data from the previous study by Henriksen et al. (2013) in which the average maternal skin carotenoids \pm SD at birth was 34000 ± 8300 . This value is 20% lower than the University of Utah Moran Eye Center clinic average value of $\sim 42,500$ Raman counts reported for the ancillary AREDS2 study ([name] et al., 2012). With power of 0.90 and alpha 0.05, a sample size of 20 was calculated for each group in order to detect and prevent a 20% decline during pregnancy. In order to accommodate subsequent ineligibility due to premature birth, low birth weight, or other problems ($\sim 10\%$) and to plan for expected noncompliance and loss to follow up ($\sim 20\%$), we intend to enroll 30 subjects in the Carotenoid Supplementation Group and another 30 in the Control Group.

The other outcome measures (maternal ocular carotenoid depletion during pregnancy, infant carotenoid status at birth, and the exploratory outcome measures of foveal maturity at birth and visual function changes during pregnancy) are not as well characterized, but we estimate that a similar sample size of 20 patients per group will be sufficient to detect differences in these indices.

Statistical Analysis Sets

The Intent-to-Treat set will include all randomized subjects who complete the Baseline Visit carotenoid status evaluations and receive study supplements. Subjects will be analyzed by the supplement arm assigned at the Baseline Visit.

A modified Intent-to-Treat set will include all randomized subjects who receive investigational product and complete carotenoid evaluations for at least one trimester study visit while utilizing study supplements.

Efficacy Analyses

The primary, secondary and exploratory efficacy analyses will be performed using the modified Intent-to-Treat subject set. Paired t-tests will compare the carotenoid status at enrollment and at the final study visit of the mothers receiving carotenoid supplementation to mothers not receiving carotenoid supplementation. We will also compare carotenoid status of infants whose mothers received carotenoid supplementation to infants of mothers without carotenoid supplementation. Significance will be set at 2-tailed $P < 0.05$. The associations between maternal and infant carotenoid status will be assessed with regression analysis.

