Subgroup analyses will be performed to assess the influences of maternal dietary carotenoid intake, compliance with study supplement use, co-existing medical conditions, BMI, infant gender, and other factors on our study results, with proper attention to the effects of multiple tests on the ability to draw conclusions.

The complete statistical analysis plan will be finalized prior to database lock, and will provide statistical methods as well as descriptions of how missing, unused and spurious data will be addressed. Summarization of study data will be prepared of subject demographics, baseline characteristics, and investigational product exposure.

Safety Analyses

Serious and unexpected adverse events will be collected from the time of the first study supplement administration until a subject completes the study or discontinues prematurely. Treatment emergent adverse events (TEAEs) are defined as those AEs that develop or worsen after the first dose of study supplement and up to 30 days beyond the last dose of study medication. The current version of MedDRA will be used to classify all AEs.

Treatment- emergent adverse events will be summarized by System Organ Class and Preferred Term, in accordance with the MedDRA coding dictionary. The number of subjects reporting each AE preferred term will be tabulated for all TEAEs and separately for those considered as related to study treatment by the Principal Investigator. The number of subjects reporting SAEs will also be tabulated. Adverse event summaries will be presented for each treatment group separately.

Adverse events will be summarized by MedDRA coding terms, and separate tabulations also will be produced for related adverse events (those considered by the Investigator as definitively drug related), serious adverse events and discontinuations due to adverse events. Findings from ophthalmologic examinations will be tabulated for changes over time on study. Separate summaries will be prepared for systemic (non-ocular) and ocular AEs, with events in the study eye and non-study eye summarized separately.

Title: Lutein & Zeaxanthin in Pregnancy (L-ZIP) - Carotenoid Supplementation During Pregnancy: Ocular and Systemic Effects

Consent Process

1. The following investigators and internal staff will obtain consent (as indicated on the Study Location and Sponsors Page):

[name]	University of Utah
[name]	University of Utah
[name]	University of Utah
[name]	University of Utah

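### Does the undefined exclusion for multiparity, with multiple gestation left unnamed, require a change to the eligibility criteria or the infant analysis?

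*Combined protocol and SAP*

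**What the plan says.** Section 3 (Participants), item 6, excludes women who "Have any conditions associated with high-risk pregnancies such as adolescent pregnancy, multiparity, current or past history of diabetes, pre-eclampsia, previous premature delivery", and the list continues with drug abuse and other significant illness. No definition or threshold for multiparity appears in the supplied text. Item 5 of the same section asks for an uncomplicated obstetric history and sets no limit on parity or number of fetuses.

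The rest of the plan assumes one infant per mother:

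- Section 3, item 4, plans for "60 mothers and 60 infants".
- Section 4 (Study Information), item 6, under Unscheduled Visits, says of a mother who delivers early that "she and her infant will remain in the study".
- Section 4, item 9, under Efficacy Analyses, states: "We will also compare carotenoid status of infants whose mothers received carotenoid supplementation to infants of mothers without carotenoid supplementation". It gives no rule for siblings.
- The subgroup paragraph in the same item lists "co-existing medical conditions, BMI, infant gender, and other factors on our study results". Neither parity nor fetal number is named.

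The objective in section 1, item 6, is to "characterize the carotenoid status of mothers during pregnancy". For recruitment, section 4, item 4, describes an electronic tool that "will be used to screen for potential patients who meet the IRB approved eligibility requirements".

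**The concern.** Read literally, *multiparity* bars some or all women who have given birth before, although the objective speaks of mothers in pregnancy without any parity limit. The same bullet also excludes women with a previous premature delivery. If any earlier birth already excludes a woman, that second exclusion has nothing left to do, which suggests that some other meaning was intended.

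The condition that would break the one-infant-per-mother structure, multiple gestation, is not named. If a twin pregnancy were enrolled, two infants sharing a mother would enter an infant comparison with no stated provision for their correlation. Infant gender would also have no single value for a mother of opposite-sex twins.

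Because records are screened against the approved criteria, the wording helps decide who is approached. At stake are the population to which the results apply and the independence of the infant observations.

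**Working it through.** **1. The plan's own sample size.** Inputs from section 4, item 9: mean maternal skin carotenoids at birth 34,000, SD 8,300, clinic average about 42,500, power 0.90, two-sided alpha 0.05. The difference is 42,500 − 34,000 = 8,500.

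n per group = 2 × [8,300 × (1.960 + 1.282) / 8,500]² = 20.04

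This agrees with the plan's statement that "a sample size of 20 was calculated for each group" (power at 20 per group is 0.899). Allowing for 10% ineligibility and 20% noncompliance or loss gives 20 / 0.70 = 28.6, or 20 / (0.90 × 0.80) = 27.8. The planned 30 covers both. Nothing in this calculation depends on what multiparity means.

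**2. What each reading does.**

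| Reading of the word | Parity of women enrolled | Previous-preterm exclusion | Multiple gestation |
|---|---|---|---|
| Any earlier birth | None | Adds nothing | Left to the open clause |
| Two or more earlier births | At most one | Still excludes a woman whose only birth was preterm | Left to the open clause |
| Slip for multiple gestation | No limit | Fully active | Excluded |

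The overlap in the first row is weak evidence of a mistake. The list is illustrative, and another of its entries, adolescent pregnancy, already largely duplicates the age limit of 18 in item 5.

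**3. Effect on the maternal comparison.** Each mother contributes her own serum, skin and macular values, however many infants she carries. Eligibility is settled before randomisation and applies to both arms. None of the three readings biases the comparison or creates dependence between mothers.

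**4. Effect on the infant comparison if one twin pair enters.** Take 20 evaluable mothers per arm and one pair in one arm, so 21 infants against 20, and 2/21 = 9.5% of that arm's infants share a mother. The within-pair correlation ρ is an assumption, taken as 0.5 to 1.0.

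For the arm with the pair, Var(mean) = (s²/n)(1 + 2ρ/n):

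- ρ = 0.5: 1 + 1/21 = 1.048, standard error ratio √1.048 = 1.024
- ρ = 1.0: 1 + 2/21 = 1.095, standard error ratio √1.095 = 1.047

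The planned analysis compares the arms, so the relevant quantity is the variance of the difference relative to its value under independence:

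- ρ = 0.5: (1.048/21 + 1/20) / (1/21 + 1/20) = 1.023, standard error ratio 1.012
- ρ = 1.0: (1.095/21 + 1/20) / (1/21 + 1/20) = 1.046, standard error ratio 1.023

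The effect on the comparison is about half the single-arm effect. With all 30 mothers per arm evaluable, it is smaller still:

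- ρ = 0.5: ((1 + 1/31)/31 + 1/30) / (1/31 + 1/30) = 1.016, standard error ratio 1.008
- ρ = 1.0: ((1 + 2/31)/31 + 1/30) / (1/31 + 1/30) = 1.032, standard error ratio 1.016

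The documents give no twin rate, so the chance of even one pair cannot be stated.

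**The case for a change.** The strongest case for a change is that the wording is operational and cheap to mend. Screening staff must decide whether a woman with an earlier birth passes, and the three readings give three different populations. Leaving fetal number to discretion is not the same as having a rule, and the subgroup list would not necessarily reveal which reading was used. The background in section 1, item 8, describes the mother transferring carotenoid stores to the infant, so fetal number could plausibly matter to the maternal outcome too.

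The point about population stands: a reader of the results will want to know whether women with earlier births were enrolled. The rest carries less weight. That more than one fetus changes maternal demand is an inference; the documents do not say it. The objective states a purpose and is not an eligibility definition, and every criterion in section 3 narrows it. Restricting a 60-mother phase II study to low-risk women is a legitimate choice. The subgroup list ends with an open category, the plan promises a summary of baseline characteristics, and a complete analysis plan is to be finalised before database lock. The application also refers to a longer protocol that is not reproduced here, so the term is known to be undefined only in the supplied text.

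**Conclusion.** This is a loosely worded criterion, possibly a clerical slip, and it calls for no change to the plan. The maternal comparison, which carries the primary outcome, is unbiased under every reading. For twins to enter, the word must be taken literally, the open high-risk clause must be judged not to cover them, and the obstetrician must agree to recruitment. If one pair did enter and was treated as independent, the standard error of the between-arm infant difference would be understated by a factor of about 1.012 to 1.023. That assumes about 20 mothers per arm, one pair, and a within-pair correlation of 0.5 to 1.0. An analyst meeting such a pair can allow for the shared mother without a prior rule and with little effect on the result.

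The remaining consequence concerns generalisability, which cannot be sized because the documents give no parity rates. Ordinary reporting covers it: how the criterion was applied, parity by arm, and any multiple gestations. The documents do not settle which meaning was intended, and none is preferred here.
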